2.1. Introduction

Nonalcoholic fatty liver disease (NAFLD) is a common and increasingly recognized disorder characterized by macrovesicular accumulation of fat in hepatocytes, usually found in association with obesity, insulin resistance, and hyperlipidemia. This condition occurs in both adults and children, and arguably represents the most common cause of liver disease in pre-adolescence and adolescence. Reports from North America, Europe, Australia, and Asia highlight the global magnitude of this problem, which appears to be increasing in proportion to prevalence of pediatric obesity. Liver histology in NAFLD may demonstrate steatosis alone, to more advanced and concerning findings of fat in concert with inflammation and fibrosis (NASH). Cirrhosis in the context of pediatric NASH is reported. Although noninvasive imaging is being developed to accurately quantitate hepatic fat content, no other noninvasive measures are identified to estimate degree of liver inflammation or fibrosis. Due to the fact that distinction between simple steatosis from NASH or NASH-related cirrhosis requires liver biopsy, relatively little is known in children about prevalence or natural history. With a paucity of longitudinal data, we do not know whether simple steatosis progresses to NASH, and which factors influence the rate of NASH progression to cirrhosis. Given that the location and extent of inflammation and fibrosis often differ between adult and pediatric NASH, extension of adult data to children is unwarranted.

Preliminary studies are published on promising therapies for NASH. With rare exception, they are open-label, uncontrolled, non-randomized pilot trials. Most studies lack baseline or end-of-treatment biopsies, and it is unknown whether long term treatment affects outcome. To attain adequate statistical power, multicenter studies are necessary.

Realizing the need for further investigation into the natural history, pathogenesis, and treatment of adult and pediatric NASH, the National Institute of Diabetes and Digestive and Kidney Diseases (NIDDK) issued a request for applications (RFA) in February, 2001 for a multi-center network (NASH CRN). Eight Clinical Centers and a Data Coordinating Center were funded by the NIDDK, with additional support from the National Institute of Child Health and Development (NICHD) allowing expansion of the pediatric component. The NASH CRN began in the summer of 2002, and many of the protocols are being finalized and undergoing institutional review. A major effort of the network is to establish a longitudinal study of suspected or proven pediatric NAFLD cases to classify, evaluate, and follow in a standard fashion. Many of the pediatric objectives of the NASH CRN are contained within this protocol.

2.2. Definition of NAFLD and NASH

NAFLD demonstrates a range of severity from the most benign (simple steatosis) to NASH resulting in cirrhosis. Although the condition was initially recognized histologically as a complication of weight loss surgery involving jejunal bypass, Ludwig later recognized the condition in obese, nonalcoholic, middle-aged adults, and coined the term “nonalcoholic steatohepatitis”¹.

Moran et al. first described the condition in children². The three reported children, two boys and one girl, were obese and without any other identifiable cause of chronic liver disease. The biopsies from these children were similar to adults with NASH, and the children demonstrated biochemical improvement of their serum aminotransferases with weight loss². Subsequent reports of children with biopsy-proven NASH have appeared from Japan³, United States^{4,5}, Canada⁶, Australia⁷, and Italy⁸. Reports now document the presence of or progression to cirrhosis in children with NASH^{6,9}.

Steatohepatitis, the histologic entity of fatty liver with inflammation and potential fibrosis, can result from a variety of metabolic, infectious, nutritional, or toxic insults. Many of these etiologies are listed in the differential diagnosis section. When steatohepatitis fits certain histologic criteria, in the context of insulin resistance or metabolic syndrome, the entity is termed NASH. Criteria for staging and grading NASH in adults have been developed¹⁰. Recently, a large analysis of NASH histology in children was performed detailing the histologic features of pediatric NASH using criteria developed for adults¹¹. Adult NASH histology differs from pediatric NASH histology, particularly with regard to extent and location of hepatic inflammation and fibrosis. We define pediatric NASH to be a biopsy-proven diagnosis of predominantly macrovesicular steatosis with evidence of either lobular or portal inflammation, evidence of cellular injury, with or without portal or pericellular fibrosis. Lipogranulomas are considered sufficient evidence of cellular injury, as the adult feature of hepatocellular ballooning or Mallory hyaline are infrequent in children.

2.3. Epidemiology

[figure not shown]
The prevalence of NASH in the pediatric population is not known. Determination of prevalence is derailed by the requirement for examination of liver histology to make a diagnosis. Estimates of prevalence can be inferred from data on the prevalence of childhood obesity, the frequency of “bright liver” on ultrasound in obese children, the frequency of abnormal ALT tests in obese children with echogenic liver, and the frequency of NASH versus simple steatosis in obese children with echogenic livers and elevated ALT who undergo biopsy.

The prevalence of child and adolescent obesity has risen dramatically over the past 20 - 30 years. Data from the National Health and Nutrition Examination Survey from 1999 - 2000 show that 14 - 16% of boys and girls between 6 and 19 years of age are obese, with obesity defined as being greater than the 95th percentile for body mass index (BMI) adjusted for age¹². This is a dramatic increase from the approximate 5% prevalence reference population found in the National Health Examination Surveys 2 and 3 in 1963 - 1965. Evident in Figure 1, the prevalence has increased with every survey since the 1960s in the United States, with no promise of plateau. The increased prevalence of obesity is blamed on a multitude of changes in American lifestyle, such as increased sedentary activities and increased caloric intake of high-fat foods and soda with refined sugars.

Given that more than 85% of children with NAFLD are obese, the next question is how many of them have imaging studies consistent with fatty infiltration by ultrasound or MRI? Franzese et al.¹³ performed ultrasonographic examinations on 72 consecutive otherwise healthy obese children with a mean age of 9.5 years. Fifty-three percent of these children exhibited a bright liver consistent with steatosis. If the prevalence of obesity in Italy were the same as in the United States, one would calculate that 8% of the pediatric population were obese with echogenic liver. In Japan, an

epidemiological ultrasonographic survey was performed on 810 school children age 4 - 12 years. No children were found with echogenic liver before age 4 years, but the overall incidence of presumed fatty liver ranged from 1.8% in girls to 3.4% in boys, 2.6% overall. Likelihood of fatty liver was best predicted by measurement of subcutaneous fat thickness¹⁴. Since ultrasound imaging is insensitive

Figure 1. Prevalence of Paediatric Obesity in the USA (1963-2000)
(>95th %ile BMI for age)

for demonstration of hepatic fat, these two studies hint that a minimum of 2.6 - 8% of children have NAFLD. Using the more sensitive technique of hepatic MRI for fat quantitation, Fishbein et al.¹⁵ found that 21 of 22 obese children aged 6 - 18 years with modest hepatomegaly demonstrated elevated fat fractions. Data from this study, in conjunction with current NHANES data, suggest that as many as 16% of American children have NAFLD.

A number of investigators performed studies of fatty liver prevalence using serum ALT as a screening tool^{3,8,16}. Whether ALT is a sensitive enough measure to evaluate NASH or NAFLD is not known, as recent evidence in adults provides ample evidence that “normal ALT NASH” occurs¹⁷. Further complicating interpretation is the realization that elevated ALT may not be due to fatty liver in some cases. Realizing that ALT as a surrogate marker in obese children likely underestimates the prevalence of NASH, it appears that 10 - 25% of obese children have abnormal ALT in these studies. Using American data for obesity prevalence, this would indicate that 1.6 - 4% of children have NAFLD.

Publications describing pediatric NASH series over the past 20 years demonstrate remarkable concordance for gender and age (Table 1). In all series, boys are reported twice as often as girls. The mean age at diagnosis in all series ranges between 11.6 and 13.5 years. Nothing is known as to why boys may be predisposed to NASH or why NASH appears at this age. Puberty is associated with dynamic changes in body composition and hormone levels. Children experience a stage of physiological insulin resistance beginning at the onset of puberty. While prepubertal children and postpubertal young adults are equally sensitive to insulin, adolescents are insulin resistant compared with either of these groups. An intriguing question about pathogenesis involves the potential role of pubertal development and sex hormones which may promote (in boys) or protect against (in girls) liver injury in susceptible individuals. Insulin resistance is reported to change at various stages of pubertal development, independent of changes in body composition with pubertal stage^{18,19}. Recently, we are noting increasing numbers of children as young as 8 years presenting with NASH in our clinics. These children are still prepubertal Tanner stage I. This observation may indicate that earlier and more severe obesity may abrogate the need for puberty-related “promoters.” Alternatively, the remarkable concordance among series in age and gender may reflect uniform selection bias.

Table 1. Demographic comparisons between studies of pediatric NASH

Study (year)	Location	# Boys/ # Girls	Age (mean)	Ethnicity
Moran et al (1983)	USA	2 / 1	12.6 y	White Non Hispanic (all)
Kinugasa et al (1984)	Japan	6 / 2	11.8 y	Asian (all)
Baldrige et al (1995)	USA	10 / 4	13.5 y	NS
Rashid et al (2000)	Canada	21 / 15	12 y	NS
Manton et al (2000)	Australia	8 / 4	11.6 y	NS
Schwimmer et al (2003)	USA	30 / 13	12.4 y	White Non Hispanic 25% White Hispanic 53% Black Non Hispanic 5% Other 17%

The series in Table 1 reflect populations of children in Asia, Australia, North America, and Europe. Races/ethnicities most often reported are Asian, White Hispanics, and White Non-Hispanic. Whether some races or ethnicities are more prone to develop NASH given a particular body mass index is unknown. Body fat distribution varies by race. In San Diego, NASH is diagnosed 3 times more commonly in Mexican-American children than in other children, despite the fact that only 24% of the children in San Diego are Hispanic. Studies have demonstrated that when adjusted for body size, Hispanic male children have significantly higher body fat and percentage fat than white or black males²⁰. Obese Hispanic peripubertal children are reported to have increased risk for development of type 2 diabetes, indicative of severe insulin resistance²¹. The increased fat in Hispanic males for a

given BMI along with the increased insulin resistance in this population coincident with puberty may explain why a proportionately larger numbers of Hispanic males are observed in the San Diego NASH population.

A summary of pediatric NASH associations is presented in Table 2.

Table 2. Pediatric NASH associations

1)	Obesity
2)	Male gender
3)	Age > 9 years
4)	Insulin resistance
5)	Hyperlipidemia
6)	Race/ethnicity

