4.2. Inclusion criteria

- Age 8 through 17 years at first screening visit
- Histologic evidence of NAFLD based on a liver biopsy obtained in the 6 months (183 days) prior to randomization, a minimum of 5% of hepatocytes with macrovesicular fat, without other etiologies for the presence of fat being identified
- Serum alanine aminotransferase elevation (ALT > 60 U/L) on two separate occasions at least 30 days apart but no more than 12 months (365 days). One of these measures must be obtained at the TONIC clinical center during screening for TONIC. The other measure may be historic (i.e., obtained prior to initiation of screening in TONIC)
- Consent
- Randomized within 16 weeks (112 days) of starting screening

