7.1. Hypotheses

Primary hypotheses:

- In pediatric nondiabetic patients with NAFLD, improvement in insulin resistance over 96 weeks of treatment with metformin will result in sustained reduction in serum alanine aminotransferase (ALT) compared to treatment with placebo
- In pediatric nondiabetic patients with NAFLD, improvement in oxidative stress status over 96 weeks of treatment with vitamin E will result in sustained reduction in serum ALT compared to treatment with placebo

Secondary hypotheses:

- Treatment with metformin or vitamin E will result in sustained reduction in serum AST and GGT compared to treatment with placebo
- Metformin and vitamin E are equally effective in achieving histologic improvement in nondiabetic children with NAFLD
- Levels of proinflammatory cytokines and serum markers for fibrosis will decrease with treatment with metformin and with vitamin E compared to treatment with placebo
- Pediatric nondiabetic patients with NAFLD have an impaired quality of life, and these scores will improve as their serum ALT improves upon treatment with metformin or vitamin E compared to treatment with placebo

Other questions to be addressed:

- We predict that insulin resistance is common in pediatric nondiabetic patients with NAFLD and will be significantly related to waist-to-hip ratio, waist circumference, serum ALT, and hepatic histology
- We predict that degree of obesity will be significantly related to hepatic histology in pediatric nondiabetic patients with NAFLD and more severe obesity (BMI or BMI z score) will be related to greater elevations in ALT and more advanced hepatic histology

- We predict that serum markers for steatosis, inflammation, and fibrosis will be significantly related to hepatic histology in pediatric nondiabetic patients with NAFLD
- We predict that worsening hepatic histology will be significantly related to a worsening in health-related quality of life in pediatric nondiabetic patients with NAFLD and more advanced histology will have worse health-related quality of life as measured by scores on the PedsQL
- We predict that improvement in the measures of insulin resistance will be significantly related to improvements in liver histology, serum ALT, and serum markers for steatosis, inflammation, and fibrosis in pediatric nondiabetic patients with NAFLD
- We predict that therapy with vitamin E will improve insulin resistance in pediatric nondiabetic patients with NAFLD

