7.2. Outcome measures

The primary outcome measure is the reduction in serum ALT after 96 weeks of treatment to either 50% of the baseline value OR to 40 U/L or lower which is sustained for at least one year. Other outcome measures are as follows:

- Reduction in serum aspartate transferase (AST) after 96 weeks of treatment to either 50% of the baseline value OR 40 U/L or lower which is sustained for at least one year.
- Reduction in serum gamma glutamyl transferase (GGT) after 96 weeks of treatment to either 50% of the baseline value OR 40 U/L or lower which is sustained for at least one year.

- Change in anthropometric measurements (weight, BMI, BMI z score, waist-to-hip ratio, waist circumference, triceps skin fold thickness and total body fat) after 96 weeks of treatment compared to baseline.
- Change in Tanner staging after 96 weeks of treatment compared to baseline.
- Change in insulin resistance (assessed by HOMA), serum vitamin E levels, cytokines, fibrosis markers, and lipid profile after 96 weeks of treatment compared to baseline.
- Change in health-related quality of life (PedsQL) after 96 weeks of treatment compared to baseline.

The histologic outcome measures require improvement in NAFLD activity after 96 weeks of treatment as determined by liver biopsies pre- and post-treatment. The histologic measures are derived from changes from baseline to the end of treatment in the NASH CRN NAFLD/NASH activity score (NAS). The NAS ranges from 0 to 8 (highest activity) and is calculated as the sum of three components of the standardized histologic feature scoring system for liver biopsies:

$$\text{NAS} = \text{Steatosis score (0-3)} + \text{Lobular inflammation score (0-3)} + \text{Hepatocyte ballooning score (0-2)}$$

Outcome measures derived from the NAS will include, but not be limited to:

- Change in NAS after 96 weeks of treatment compared to baseline NAS
- Changes in fibrosis, steatosis, lobular inflammation, hepatocyte ballooning and other specific feature scores from the histologic scoring system after 96 weeks of treatment compared to baseline
- Improvement in NAS and in specific features defined as any improvement in the corresponding scores

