Analyses for outcomes related to other secondary hypotheses will be conducted in two ways. Improvement will be analyzed both as a binary outcome (improved vs. not improved) and also in terms of the numerical change in the outcome. Binary outcomes will be compared using the Mantel-Haenszel χ^2 test for stratified 2x2 tables. Numerical changes will be analyzed by descriptively comparing the between-treatment group differences in mean and median changes; P-values will be derived from Wilcoxon rank sum tests for comparison of the distribution of changes in each group. If concerns about confounding arise, logistic regression models for improvement outcomes and linear regression models for numerical change outcomes will be used to correct for the confounding. Analyses for secondary hypotheses will generally involve three separate analyses, one for each treatment group comparison: metformin vs. placebo, vitamin E vs. placebo, and metformin vs. vitamin E. No adjustments for multiple comparisons will be applied to the secondary hypotheses; however, any significant findings must be interpreted taking into account the strength of the finding and its biologic plausibility.

Other questions to be addressed:

A series of other questions of interest were listed in Section 7.1. Analyses related to these questions will involve a mix of appropriate exploratory and confirmatory analyses, similar, but not limited to those described for the primary and secondary hypotheses.

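### HOMA change in 8-17-year-olds is compared between arms without pubertal stage, which costs precision; the exploratory HOMA-to-liver relation has no pubertal covariate named and could be confounded

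*Supplement*

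**What the plan says.** - **Background, Section 2.3.** Prepubertal children and postpubertal young adults are described as equally insulin sensitive, and adolescents as resistant compared with both. It adds that "Insulin resistance is reported to change at various stages of pubertal development, independent of changes in body composition with pubertal stage". The same paragraph asks, as an open question, about a role for "pubertal development and sex hormones which may promote (in boys) or protect against (in girls) liver injury in susceptible individuals".
- **Population, Section 4.2.** "Age 8 through 17 years at first screening visit".
- **Outcome, Section 7.2.** "Change in insulin resistance (assessed by HOMA), serum vitamin E levels, cytokines, fibrosis markers, and lipid profile after 96 weeks of treatment" is listed among the other outcomes. The design synopsis places insulin resistance indices under secondary outcomes.
- **Exploratory question, Section 7.1.** Under the other questions, the protocol predicts that "improvement in the measures of insulin resistance will be significantly related to improvements in liver histology, serum ALT, and serum markers for steatosis", among other markers.
- **Analysis, Section 7.3.** Numerical changes are compared between arms by Wilcoxon rank sum tests. Adjustment is conditional: "If concerns about confounding arise, logistic regression models for improvement outcomes and linear regression models for numerical change outcomes will be used". No covariate is named. The other questions are left to unspecified exploratory and confirmatory methods, similar but not limited to those already described.
- **Tanner stage.** It is recorded at screening visit 1 and at weeks 48, 96 and 120 (Sections 5.2 and 5.4). Its change is an outcome (7.2), and maturation is predicted to be similar across arms (7.1). It is not named as a covariate or stratum anywhere. Randomization is stratified by clinical center only (3.2).

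**The concern.** Over 96 weeks, some children will enter the insulin-resistant stage of puberty and others will leave it. HOMA then rises in the first group and falls in the second for reasons unrelated to study drug. This touches two analyses differently.

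In the comparison between arms, pubertal movement is extra variance. Part of it is predictable from the stage at baseline, which is on file for every child, but the planned test does not use it.

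In the patient-level relation between HOMA change and liver change, randomization gives no protection. If puberty also moves ALT or histology, it is a common cause of both sides. It could produce a correlation where there is no link, or hide a true one. Similar Tanner change across arms would not cure this, because the confounding acts between children, not between arms. At stake is whether a published statement about mechanism can be trusted, not whether either drug is found to lower ALT.

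**Working it through.** **The plan's own figure.** The only computed design figure is 60 per group for ALT response (Section 7.5), and it is not in dispute. With rates 0.20 and 0.50, mean 0.35, two-sided alpha 0.025 and 90% power: n = [2.2414 × √(2 × 0.35 × 0.65) + 1.2816 × √(0.16 + 0.25)]² / 0.30² = (1.512 + 0.821)² / 0.09 ≈ 60.5, so 61. Power at 60 per group is 0.898. The plan gives no power figure for HOMA.

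**Assumed inputs.** The documents give no size for the effect of puberty on HOMA or the liver, and no transition rates. The following are assumptions:
- 162 children with paired data (180 less the 10% ceiling for missing data in Section 7.4), or 54 per arm.
- Pubertal transition g = +1 (entering the resistant stage), 0 or −1 (leaving), with probabilities 0.3, 0.4 and 0.3, so Var(g) = 0.6.
- HOMA change = h·g + noise and liver change = a·g + noise, each noise term with SD 1, h from 0.5 to 1.0 and a from 0.25 to 0.5.

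**Comparison between arms.**
1. Share of HOMA-change variance due to puberty = 0.6h² / (1 + 0.6h²), which is 0.15/1.15 = 13% at h = 0.5 and 0.6/1.6 = 37.5% at h = 1.0.
2. Approximate power for a difference of 0.5 noise SD is Φ(0.5/σ × √(54/2) − 1.96). With σ = √1.15 this is 68%; with σ = √1.6 it is 54%. If all pubertal variance were removed (σ = 1) it would be 74%. That is a ceiling, because baseline stage predicts only part of the transition.
3. In simulation over assumed shifts, replacing the Wilcoxon test by a model with baseline Tanner stage and sex raised power from 67% to 71% at the mild end and from 47% to 61% at the strong end. These values move with the assumed shift and mix of stages.
4. With no true drug effect, a separate simulation (60 per arm) rejected 4% to 6% of the time with or without puberty in the model. There is no bias.

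**Relation of HOMA change to liver change, with no true link.**

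Expected correlation: r = 0.6ha / √[(1 + 0.6h²)(1 + 0.6a²)].

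| Assumption about puberty and liver | r | P<0.05, unadjusted |
|---|---|---|
| Same sign in all children, following the rise and fall of HOMA | 0.07 to 0.22 | 14% to 82% |
| Opposite sign by sex, two boys per girl | 0.02 to 0.07 | about 6% to 16% |
| Liver moves one way as puberty advances | 0 | about 5% |

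The second row is the first multiplied by (2 − 1)/3. The third is zero because entering and leaving are equally frequent in this setup, so their contributions cancel.

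Masking is possible too. With N = 180, a true slope of 0.2 and opposing pubertal correlations of ±0.3, power was 31% unadjusted against 74% adjusted. At ±0.4 it was 8% against 77%.

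**Which adjustment works.** Tanner stage only advances, so entering and leaving the resistant stage are both positive steps with opposite effects on HOMA. In simulation, a model with baseline stage plus linear Tanner change left 5% to 27% false positives. Categories formed from baseline and week-96 stage together brought the rate to about 5%.

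**The case against.** The strongest reply is that little of this touches anything the trial is built to decide.

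- **The primary hypothesis is worded as a mechanism, so a reader might infer that it is compromised.** The documents do not support that. Section 7.3 tests it by a Mantel-Haenszel comparison of ALT response between randomized arms, and HOMA does not enter.
- **A reader might infer that the HOMA comparison is biased.** It is randomized. Puberty adds noise and chance imbalance, nothing systematic.
- **A reader might infer that the plan relates HOMA to the liver while excluding pubertal stage.** It states no model for that question, excludes no covariate and permits regression. This point stands: the gap is an unnamed covariate in an exploratory analysis. But the trigger for adjustment is undefined, and the need is foreseeable from Section 2.3.
- **A reader might treat puberty as an established cause of liver change.** Section 2.3 only poses the question. It also suggests that early, severe obesity may bypass puberty-related promoters and that the age and sex pattern may be selection bias.
- **A reader might expect false positives of 14% to 82%.** That range needs one sign and a rise-then-fall liver effect in every child. Section 2.3 says neither, and suggests opposite directions by sex.
- **A reader might conclude that a child entering puberty is bound to count as not improved.** No HOMA improvement cut-off is defined. Under the assumptions above, 16% to 31% of such children would still show a fall in HOMA with no drug effect: Φ(−1.0) to Φ(−0.5).

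Section 7.3 also attaches the Wilcoxon test to the secondary hypotheses, and HOMA is not named among these. Because the synopsis lists insulin resistance as a secondary outcome and no other method is given, the Wilcoxon test is the natural reading.

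**Conclusion.** The point holds in a limited form. By the protocol's own account, pubertal stage moves insulin resistance independently of body composition, and the stage is recorded; leaving it out of the HOMA comparison discards precision at no benefit. The gain from baseline stage and sex is about 4 to 14 power points for a 0.5 SD effect, under assumed pubertal shifts. The comparison remains valid without it.

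For the exploratory relation of HOMA change to ALT and histology change, confounding by pubertal transition is possible but not shown. It requires an effect of puberty on the liver, which the protocol treats as a question. Depending on the form assumed, the false-positive rate runs from the nominal 5% to far above it, so no single figure should be quoted. The primary ALT tests and the sample size are unaffected.

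**What to change.** Amend Section 7.3 in two places.

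1. **HOMA change between arms.** Replace the unadjusted test by a regression, on log or ranked HOMA if skewed, with treatment, baseline HOMA, sex and baseline Tanner stage as a categorical covariate. Use no Tanner data from after randomization in this model.
2. **Exploratory relation of HOMA change to ALT and histology change.** Include treatment arm, sex and pubertal transition coded from baseline and week-96 Tanner stage together: entering, remaining in or leaving the resistant stages, or a baseline-by-change term. Add a sex-by-transition term, since Section 2.3 suggests opposite directions in boys and girls. Do not rely on linear Tanner change alone. Base any statement about mechanism on this model.

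The cost is a few sentences and a few degrees of freedom. Some transition-by-sex cells may be small, so sparse categories should be merged by a rule fixed in advance. No new visit, measurement or patient is needed.
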